10.1. Annual Safety Reporting

The CI will send an Annual Progress Report to the REC and the sponsor using the HRA template on the anniversary of the REC "favourable opinion".

11. Public involvement

No specific PPI has been done for this project due to its commercially translational nature, however, the objective of this study is well aligned to a key research priority of the European Asthma and Research Innovation Partnership (EARIP) to "Identify, understand and better classify the different forms of asthma, their progression, and effect on airway inflammation and the immune system", these priorities were developed in close consultation with patient groups.

12. Data handling and record keeping

12.1. Data management

Clinical data will only be accessed by clinical site teams via the secure electronic medical records on NHS computers; and no identifiable information will be removed. All patient identifiable data will be anonymised and stored on secure NHS systems, which are password encrypted and only accessible by clinical staff.

Once data is anonymised, it will be moved using password-protected USB drives or secure nhs.net to nhs.net emails to university computers, based in the Blizard Institute, for data analysis. Data used on non-NHS systems, *e.g.* laboratory computers for data analysis, will be anonymised to protect confidentiality. Each participant will be assigned a study code that is separate from their identifiable data.

No personally identifiable information will leave the hospital. Consent forms will be stored in the study file in a locked cabinet at each study site. The only link between participant study codes and identifiable information will be a spreadsheet at site, which will be password-protected and held on secure NHS computers and in the secure site-file for NHS sites.

All NHS investigators undergo regular training in data confidentiality and information governance, in line with the trust policy on confidentiality. All investigators will be Good Clinical Practice or UK policy framework for health and social care research certified by the start date of the project.

All laboratory data generated by the study will be stored securely with a full audit trail.

12.2. Source Data

Source data (original data generated by study)

- Participant demographics (age and gender)
- · Medical history of eczema, asthma, allergies, rhinitis
- Clinical reason for surgery
- Medication history (topical, nasal therapy or systemic corticosteroids; biologic therapy)
- Latest blood eosinophil count, FeNO (where available)

Source documents (data not generated by study)

· Patient medical records

12.3. Confidentiality

Information related to participants will be kept confidential and managed in accordance with the Data Protection Act, NHS Caldecott Principles, The Research Governance Framework for Health and Social Care, and the conditions of Research Ethics Committee Approval. Patients will be required to give their informed consent to allow site investigators to access their clinical records. Participants will be assigned a unique (alpha-numerical) identification code that will be used to label the sample. Only the study investigators will have access to the code. No identifiable participant data will be taken off secure NHS computers.

12.4. Record retention and archiving

When the research study is complete, study records will be kept for a further 5 years in accordance with the Research Governance Framework and Trust Policy. Records will be deposited in the Trust Modern Records Centre (Barts Health NHS Trust) and equivalent for other NHS sites. Consent forms will be stored in locked cabinets only accessible by the site investigators and researchers.

The lead investigator and lead researcher will have access to the samples and all anonymised research data for the duration of the study. All data generated will be anonymised and will be analysed at the Blizard Institute, Queen Mary's University of

London by the Lead Investigator and the research team associated with the study and collaborators. The research data will be archived for 5 years according to Queen Mary University of London/ Barts Health NHS Trust policy. The data will be archived in the Modern Records Facility, [name]

13. Laboratories

13.1. Central and local laboratories

Sample processing and analysis will be performed in the Blizard Institute, [name]. All research staff involved in the processing of the samples will have Good Laboratory Practice training.

13.2. Sample preparation and collection

Details of the sample collection (Sample ID and date of collection) will be recorded in a laboratory notebook as soon as samples arrive at the laboratory along with details of sample processing and storage. Patient identifiable information will not be made available to the research team.

13.3. Laboratory procedures

All laboratory procedures will be conducted purely for research purposes and not form part of any clinical care. Initial sample processing will be undertaken at the Blizard Laboratories, QMUL. Further pseudo-anonymised sample analyses by be undertaken by external collaborators where the assay cannot be conducted at QMUL.

Tissue samples will be dissociated by mechanical disruption. Immune cells may be isolated or enriched with magnetic beads and/or flow cytometry as per experimental protocols. Immune cells will be processed for single cell RNA sequencing using the 10X genomics platform at the genome centre core facility at the Blizard Institute. For bulk antibody repertoire analysis the tissue will be homogenized and RNA isolated from the homogenate. Antibody sequencing libraries will be generated by targeted PCR and then sequenced at the genome centre core facility at the Blizard Institute.

Subject to initial experiments being successful, B cell specificity will be interrogated using dCODE Klickmer oligonucleotide-barcoded antigens in later experiments, using antigens from viruses (e.g. covid, rhinovirus) and bacteria (e.g. Staphylococcus aureus enterotoxins [Chen et al. 2017]) known to trigger flares of nasal polyp inflammation and asthma exacerbations. dCODE oligonucleotide-barcoded putative auto-antigens,

identified as part of the ongoing GSK-funded IDEA ISS, will also be examined to compare tissue to blood B cell auto-antibody expression, and whether those B cells are IL-5 responsive.

Specific sequences will be analysed using an established computational pipeline based in the Immcantation packages (Nouri & Kleinstein. Bioinformatics 2018). Clonally-related B cell discerned by sequence identity (same VDJ gene rearrangement and CDRH3) and clonal lineages will be reconstructed. The properties of individual antibody repertoires will be analysed to quantify (per subclass) i) average clone sizes to provide a measure of clonal expansion, ii) clonal relatedness to other subclasses, and iii) frequencies of somatic hypermutation. These measures will then be compared between different patient groups (ex vivo WP) or stimulation condition (in vitro WP).

Samples may be sequenced *ex vivo* or after *in vitro* cell stimulations as described in the Study Design.

Other laboratory techniques that may be undertaken within the planned experimental work package:

- B cell flow-cytomtery
- o ELISA for immunoglobulin proteins
- B-Spot cultures (B cell enzyme-linked immunosorbent spot (ELISpot))

Genomic DNA will not be analysed.

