5.1. Research Questions

What are the actions of IL-5 and its blockade on tissue resident B cells in nasal polyps? Questions that follow include:

- Does IL-5 contribute to class-switching whether class of immunoglobulin secreted differs in the presence of IL-5 / blockade?
- Does IL-5 differentially contribute to survival of B cells expressing B cell receptors (immunoglobulins) of different classes and subclasses?
- Does IL-5 / blockade affect affinity maturation of B cells, necessary for optimal antibody responses to new and evolving pathogens?
- Are there clonotypes evident in nasal tissue of patients with nasal polyps selective for eosinophilic disease?

- Are there clonotypes evident in nasal tissue of BCR specific for putative auto-antigens (extending findings of current GSK-funded IDEA study that will be analysing BCR repertoires in blood from characterised patients)? - Do B cells expressing these clonotypes express IL-5Ra and respond to IL-5?

6. Study population

WP1: We will recruit the following:

Patients undergoing nasal polyp resections and tonsillectomy (n=10)

WP2: We will recruit to the following groups:

- Nasal polyps not on biologics (n=6)
- Nasal polyps on anti-IL-5(R) biologics (n=6)
- Control patients without nasal polyposis (n=6)

We will use purposive sampling in our recruitment of the nasal polyps not-on-biologics and control patients groups to attempt to match patient characteristics (i.e. asthma status, age and gender) to the patients with polyps on biologics, which is predicted to be the more difficult group to recruit. Control patients will predominantly be patients undergoing nasal surgery for deviated nasal septa (structural rather than immunological pathology).

Research tissue from a single patient may be used for both WP1 and WP2.

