Nasal tissue will be collected from patients with nasal polyps not on biologics (n=6), with polyps on anti-IL-5(R) biologics (n=6) and control patients without nasal polyposis (n=6) undergoing clinically-indicated nasal surgery. Samples will be dissociated, and cells labelled with oligonucleotide-barcoded antibodies to CD20 and IL-5Ra. Single-cell B cell receptor (BCR) sequencing will be undertaken in the QMUL Core Genomics facility, and BCR repertoire (i.e. immunoglobulin repertoire) analysed to identify the immunoglobulin class, subclass and antibody sequence of tissue B cells from the three patient groups, stratified by IL-5Ra expression. Complementary bulk RNA sequencing with BCR-specific primers will be conducted to increase the depth of sequencing and enable further comparisons between groups.

These samples may additionally be examined by bulk RNA BCR sequencing after *in vitro* stimulation as per WP1. Optional collection of blood and nasoabsorption samples will be conducted at selected sites similar to WP1.

8. Study procedures

Invitation to Participate:

Invitation to Participate will be by members of the clinical team who will provide potential participants with a copy of the Participant Information Sheet (PIS) in advance of their scheduled surgery.

Patients will be identified by participating respiratory clinical teams, from those attending severe asthma services and undergoing nasal surgery as part of their comprehensive airways management, Additional patients will be identified by participating ENT teams, from those attending for surgery for nasal polyps, turbinectomy and septoplasties and reconstructive surgery.

Informed Consent Procedures and Screening:

On the day of scheduled surgery, potential participants interested in the study will be given the opportunity to ask questions from a GCP-trained member of the research team who may or may not be a member of the clinical team treating the participant. After questions have been answered potential participants will be asked to complete the written Informed Consent. Consenting participants will then be briefly screened to check they fulfil inclusion/exclusion criteria.

Data Collection (CRF):

A member of the site clinical team will complete the case report form (CRF) which contains only anonymised information but with a study code to link to patient samples (and to Consent Form for governance purposes). See Source Data section.

Sample Collection:

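### Section 13.3 compares average clone size between groups and culture conditions with no control for the number of cells or sequences sampled, so a difference in yield can look like clonal expansion

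*Protocol*

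**What the plan says.** Section 13.3 (Laboratory procedures) defines a clone by sequence: "Clonally-related B cell discerned by sequence identity (same VDJ gene rearrangement and CDRH3". Using an "established computational pipeline based in the Immcantation packages", it will quantify three properties of each repertoire per subclass: "average clone sizes to provide a measure of clonal expansion", clonal relatedness to other subclasses, and somatic hypermutation frequency. It then fixes their use: "These measures will then be compared between different patient groups (ex vivo WP) or stimulation condition (in vitro WP".

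The amount sampled is not fixed anywhere. On input, section 13.3 says "Immune cells may be isolated or enriched with magnetic beads and/or flow cytometry as per experimental protocols". On depth, section 7 (Study design, ex vivo work package) says "Complementary bulk RNA sequencing with BCR-specific primers will be conducted to increase the depth of sequencing", which raises depth but does not equalise it. Section 9 (Statistical considerations) leaves the choice between parametric and non-parametric tests open and does not mention cell or sequence counts. Section 6 sets six patients in each of the three ex vivo groups.

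**The concern.** A clone's size in the data is the number of its members that were sampled. With few sequences, nearly every clone is seen once and the average sits near 1. With more sequences, the same clones are seen repeatedly and the average climbs. A comparison of averages is therefore partly a comparison of how much was sampled.

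The protocol gives its own reasons to expect unequal sampling:

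- **Tissue.** "Control patients will predominantly be patients undergoing nasal surgery for deviated nasal septa" (section 6), so control tissue is mostly septal rather than polyp.
- **Treatment.** Section 4.1 raises possible depletion of B cells that express the IL-5 receptor.
- **Subclass.** Section 5.1 asks whether IL-5 affects B-cell survival differently by class and subclass.

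The last of these matters most. The primary objective is whether IL-5 blockade shifts the relative expression of classes and subclasses. If a subclass becomes more abundant, more of its sequences are sampled and its average clone size rises with no change in clonal structure. One effect could then be reported as two.

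Clonal relatedness between subclasses shares the weakness, because the chance of finding one clone in two subclasses grows with the number sampled from each.

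**Working it through.** The protocol gives no clone-size figure, cell yield or sequencing depth, so there is no stated figure to reproduce. Only the group size of 6 comes from the protocol (section 6). Clone numbers, clone frequencies, depths, donor variation and the two-sided 5% level are assumptions.

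**Step 1. Dependence on depth with the clones held fixed.** For clone frequencies p_i and n sampled sequences, the expected mean clone size is approximately n / Σ[1 − (1 − p_i)^n].

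Check by hand with 2,000 equal clones:
- n = 200: 1 − (1 − 1/2,000)^200 = 0.0952; 2,000 × 0.0952 = 190.4 clones seen; 200 / 190.4 = 1.05.
- n = 2,000: 1 − (1 − 1/2,000)^2,000 = 0.632; 2,000 × 0.632 = 1,264 clones seen; 2,000 / 1,264 = 1.58.

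The same formula with p_i proportional to rank^(−a):

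| Clones, exponent a | n = 200 | n = 500 | n = 1,000 | n = 2,000 |
|---|---|---|---|---|
| 2,000, equal | 1.05 | 1.13 | 1.27 | 1.58 |
| 2,000, a = 0.8 | 1.31 | 1.55 | 1.84 | 2.32 |
| 2,000, a = 1.0 | 1.70 | 2.09 | 2.52 | 3.17 |
| 20,000, a = 1.0 | 1.43 | 1.62 | 1.82 | 2.06 |
| 1,000,000, equal | 1.000 | 1.000 | 1.000 | 1.001 |

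The average rises with n wherever clones recur. The rise is negligible when almost every sequence is a singleton.

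**Step 2. Subclass share.** With 2,000 clones and a = 0.8, a subclass that goes from 100 to 400 sequences with unchanged clones moves from 1.20 to 1.48.

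**Step 3. Effect on a 6 v 6 comparison with no true difference.** Mann-Whitney test, mean exponent 0.8, log-depth SD 0.4 within groups, 400 simulated studies per setting (200 in the last row):

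| Assumed donor variation | 250 v 500 sequences | 200 v 1,000 sequences |
|---|---|---|
| 5,000 clones in every donor, exponent SD 0.05 | 35% | 99% |
| 5,000 clones, exponent SD 0.1, log-clone-number SD 0.5 | 15% | 66% |
| 5,000 clones, exponent SD 0.2, log-clone-number SD 1.0 | 9% | 28% |
| 5,000 clones, exponent SD 0.3, log-clone-number SD 1.0 | 6% | 20% |
| 50,000 clones, exponent SD 0.2, log-clone-number SD 1.0 | 5% | 10% |

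These rates carry simulation error; at 6% with 400 runs the standard error is √(0.06 × 0.94 / 400) = 1.2 percentage points. Repeat runs at 5,000 clones gave values up to 40% at two-fold with near-identical donors, and as low as 7% at two-fold and 17% at five-fold with the most variable donors. At 500 v 500 the rate was 4% to 5%.

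With 2,000 clones and no donor variation at all, the rate was 68% to 72% at 500 v 1,000 and 97% to 100% at 500 v 2,000. Identical donors are an upper extreme, not a realistic case.

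**Step 4. After equalising depth.** When all 12 samples are drawn to one common depth, the rate falls to between 2% and 7% across the settings run.

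**The case against.** The strongest reply is that silence is not error. The protocol does not say the averages will be taken at unequal depth, and subsampling is the kind of detail a statistical analysis plan or analysis script may hold. A reader might infer from section 13.3 that the sponsor has ruled out normalisation; the text does not support that. What remains is that the protocol names a depth-dependent measure, assigns it to comparisons, and nowhere conditions it on equal sampling.

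Second, a reader might infer that the groups will differ in B-cell number and so will show false expansion. No yields are documented. In the in vitro work package, B cells are isolated before culture, so conditions can start from equal numbers, and later proliferation may be real expansion. The bias arises only where yield or subclass share does differ.

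Third, the size depends heavily on how alike the donors are, as step 3 shows. This stands, and it is why only a range can be given.

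Fourth, a reader might extend the point to clonotypes shared between donors, arguing that 12 pooled polyp donors form more pairs than 6 controls. The protocol states no such analysis. It keeps three groups of six and, for its secondary objective, compares tissue clonotypes with blood and other libraries.

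Finally, clone size is not named in the objectives or research questions, and section 9 calls the study hypothesis-generating. That lowers the weight of the point. It does not remove it, because this is a systematic bias rather than low precision, and it can generate a false hypothesis.

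**Conclusion.** The point holds in a limited form. As written, average clone size per subclass mixes clonal expansion with the number of cells or sequences sampled, and the protocol gives reasons to expect that number to vary between groups. Where it does, a 6 v 6 comparison with no true difference gives false positives in about 7% to 40% of studies at a two-fold depth difference and 17% to 99% at a five-fold difference, against about 5% at equal depth. The rates are lower for very diverse repertoires. They rest on assumed clone distributions, depths and donor variation. The direction of the bias does not depend on those choices; its size does.

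This should be corrected before groups are compared. It does not call into question the comparison of class and subclass shares under the primary objective.

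**What to change.** Add to section 13.3 that average clone size and clonal relatedness between subclasses are compared after repeated subsampling of every repertoire in a comparison to one common number per subclass, counted in cells for single-cell data and in unique molecules for bulk data, and averaged over the draws. State a minimum count below which a subclass is not reported for a sample on these measures, and report the counts. The counts matter in their own right: proliferation that multiplies all clones equally leaves their frequencies unchanged and will not show at a common depth.

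The change needs a sentence or two of protocol text and a little analysis code, with no new samples or assays. The cost is that some data from deep samples go unused, and sparse subclasses may not be reportable on these measures in some patients, which is felt in groups of six. A very low common depth also pushes the average towards 1 and leaves little room to see true expansion, so the minimum should be set with that trade-off in view.

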13.4. Sample storage and transfer

All samples will be processed within 24 hours of collection and processed sample material (e.g. excess RNA) stored at -80°C in the laboratories within the Blizard Institute. Samples will be stored in sample preservation buffer overnight prior to processing. The details of the stored samples will be recorded in an electronic database in an anonymised form.

14. Safety reporting

The only patient contact in this study is the consent process and the sample donation of residual tissue collected as part of clinical care. As such study-attributable Adverse Events (AE) and Serious Adverse Events (SAE) are extremely unlikely. In the event of an AE or SAE then this will reported to the CI by any research team members, and escalated as appropriate by the CI. Unsolicited GSK product related events will be reported according to local reporting regulations.

Notification and Reporting of Serious Adverse Events:

Serious Adverse Event (SAEs) that are considered to be 'related' and 'unexpected' will be reported to the sponsor within 24 hours of learning of the event and to the Main REC within 15 days in line with the required timeframe.

In addition to reporting to the sponsor, any SAEs (anonymised information) will be reported to the funder.

15. Monitoring and auditing

The Sponsor or delegate retains the right to audit any study, study site or central facility. In addition, any part of the study may be audited by the funders where applicable.

The study will be monitored according to our sponsor's SOP (QMUL).

16. Study committees

All data generated as part of this study will undergo regular review by an informal committee within the research department of the Chief Investigator, including external collaborators. This committee will comprise the Chief Investigator and researcher(s) involved in the study as well as independent senior members of the Department who will review and discuss data and research outcomes.

17. Finance and funding

This study is funded by a research grant from GSK.

18. Insurance and indemnity

The insurance that Queen Mary has in place provides cover for the design and management of the study as well as "No Fault Compensation" for participants, which provides an indemnity to participants for negligent and non-negligent harm.

19. Dissemination of research findings

